8.2. Plan of analysis

Subjects that are transferred to another ICU in the first three calendar days of ICU admission will be excluded from analysis. Subjects that are transferred to another ICU after the first three calendar days, but before seven days are excluded from analysis of the secondary endpoints. Patients admitted due to pancreatitis, burns, diabetic ketoacidosis, severe rhabdomyolysis and sub-arachnoid bleeding will be analyzed separately and excluded from analysis if less than 30 subjects are included in each category. Subjects diagnosed with sepsis or ARDS during the first three calendar days of ICU admission will be part of a subgroup analysis. Associations with outcomes will be assessed through regression modelling. Time to event variables are analyzed using Cox regression and visualized by Kaplan–Meier plots. For each analysis proposed, a complete statistical analysis plan will be prepared, finalized and made available before starting the analyses. Statistical analyses are conducted using R (www.r-project.org). A *P*–value of less than 0.05 is considered statistically significant.

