1. SUMMARY

Rationale

The worldwide practice of fluid and vasopressor therapy in critically ill invasively ventilated patients is uncertain. Indeed, it is unclear whether there is a difference in fluid and vasopressor therapy in these patients between Low- and Middle-income Countries (LMICs) and High-income Countries (HICs).

Objective

To determine various aspects of fluid and vasopressor therapy in critically ill invasively ventilated patients in LMICs and HICs.

Hypothesis

There is substantial worldwide variation in practice of fluid and vasopressor therapy in critically ill invasively ventilated patients.

Study design

International, multicenter, observational study in critically ill invasively ventilated patients; data are captured during a predefined period per geographic region or country.

Study population

Critically ill invasively ventilated patients.

Main study parameter/endpoint

The primary outcome is a composite of various aspects of fluid therapy, including total volumes of types of fluids administered in the first three days after start of invasive ventilation and total volume of fluids infused in the first seven days after start of invasive ventilation. Secondary outcomes include timing of start, type, and duration of continuous administration of vasopressors; timing of start, infusion time and types of administered diuretics; daily urine output and cumulative fluid balances; and typical ICU outcomes, like duration of ventilation, lengths of stay in ICU and hospital, and mortality in the ICU and hospital, and at day-28, -60 and -90.

Nature and extent of the burden and risks associated with participation, benefit and group relatedness

Because of the observational design of the study using routinely collected data, there is no additional burden for the patient. Collection of data from ICU charts or electronic medical records systems is of no risk to the patients.

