5.2. Inclusion criteria

- admitted to a participating ICU;
- receiving invasive ventilation within 3 days of ICU admission; and
- duration of ventilation > 24 hours;

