6. METHODS

6.1. Study parameters

6.1.1. Primary parameter

- Quantity, timing and type of intravenous fluids administered.

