6.2.3. Data to be collected

The following data will be collected for all enrolled patients admitted to ICU during the screening period. Day 0 is defined as the day of initiation of invasive ventilation. Day 1 is defined as the first full calendar day after initiation of invasive ventilation. In patients that are not invasively ventilated at ICU admission day -3 to -1 are defined as the days before intubation but after ICU admission.

A. At ICU admission;

- Gender, male/female/other;
- Age, years;
- Weight, kg;
- Length, cm;
- Ethnicity, Black, East Asian, Indigenous (First Nations, Inuk/Inuit, Métis), Latin American, Middle Eastern, South Asian, Southeast Asian, White;
- Reason for ICU admission;
- Traumatic brain injury?;
- Sub-arachnoid hemorrhage?
- Date of ICU admission;
- Date of start of invasive ventilation;
- Did the patient receive non-invasive ventilation or high-flow nasal oxygen prior to intubation, if so: on which day?;
- Serum creatinine, $\mu\text{mol/L}$ or mg/dL , lowest in the last year, if available; and
- If the reason for ICU admission was burns: what was the cause of the burn and how much total body surface area is affected by the burns
- If the reason for ICU admission was sepsis, what was the focus of the sepsis (e.g. respiratory, abdominal)

B. On day 0;

- Type and volume, ml, of each fluid infusion (including medication and parenteral nutrition);
- Type and volume of oral fluids;
- Anuria ≥ 12 hours?, yes/no;
- Urine output, ml, over 24 hours;
- Extracorporeal life support, venoarterial/venovenous/no;

- Renal replacement therapy, yes/no, if yes;
 - Volume extracted by ultrafiltration, ml, over 24 hours;
- Cumulative fluid balance, ml;
- Loop diuretics given, yes/no, if yes;
 - Furosemide, yes/no, if yes;
 - (if no furosemide used) Bumetanide, yes/no, if yes;
 - (if no bumetanide or furosemide used) Torasemide, yes/no, if yes;
 - (if no Torasemide, bumetanide, furosemide used) Edecrin, yes/no;
- Additional diuretic given (thiazide, carbonic anhydrase inhibitor or mineralocorticoid antagonist), yes/no;
- Serum creatinine, $\mu\text{mol/L}$ or mg/dL , at a convenient fixed time point;
- Serum hemoglobin, $\mu\text{mol/L}$ or mg/dL , at a convenient fixed time point;
- Serum albumin, at a convenient fixed time point;
- Vasopressors initiated, yes/no, if yes;
 - Time between ICU admission and initiation of vasopressors, hours;
 - Drug(s) used as vasopressor;
- Mean arterial pressure (MAP) mmHg, at a convenient fixed time point;

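### One transfer rule, timed from ICU admission, governs endpoints timed from the start of ventilation; it lets incomplete primary volumes in and throws out secondary data already recorded

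*Protocol*

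**What the plan says.** Section 8.2 (Plan of analysis) has two transfer rules. Subjects "transferred to another ICU in the first three calendar days of ICU admission will be excluded from analysis". Those "transferred to another ICU after the first three calendar days, but before seven days are excluded from analysis of the secondary endpoints". The first rule counts from ICU admission; the second names no origin for its seven days.

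The endpoints run on another clock. The Summary (Section 1) defines the primary outcome as a composite that includes two volume components. The shorter one is "total volumes of types of fluids administered in the first three days after start of invasive ventilation". The longer one, on the same clock but without the breakdown by type, is "total volume of fluids infused in the first seven days after start of invasive ventilation". Section 6.2.3 states: "Day 0 is defined as the day of initiation of invasive ventilation". Section 5.2 admits patients whose ventilation begins up to 3 days after ICU admission, and Section 6.2.3 provides study days -3 to -1 for them.

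On data capture, Section 6.2.3 records each fluid infusion on days 0 to 2. It records a daily total on days 3 to 7, stopping at ICU discharge. Vasopressor drugs are recorded daily. The date and route of vasopressor initiation are recorded at day 7 or ICU discharge. Section 6.1.2 lists vasopressor start, route and type as secondary, together with fluid balance, urine output, ventilation duration, lengths of stay and all mortality endpoints.

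**The concern.** A transfer rule should remove a patient from an endpoint only when transfer makes that endpoint unobservable. This one does not follow that principle, in four respects.

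- The three-day filter does not guarantee the three-day fluid window, because the two are counted from different origins.
- Patients transferred after day 3 but before day 7 stay in the primary analysis, although part of their seven-day volume cannot be observed.
- The same patients are removed from secondary endpoints that were fully recorded before they left.
- They are removed from mortality because of an event after enrolment that requires being alive. A patient who dies on day 5 stays in the denominator, one transferred alive on day 5 leaves it, and one transferred after day 7 stays.

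At stake are the description of fluid volumes, which is the primary aim, the completeness of the vasopressor results, and the mortality estimates and association models.

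**Working it through.** **1. Clock.** Inputs: transfer cut-off in ICU calendar days (Section 8.2); day 0 is the day ventilation starts (Section 6.2.3); lag k from ICU admission to day 0 of 0 to 3 days (Section 5.2). Call the admission day ICU day 1, so day 0 falls on ICU day 1 + k. For a transfer on ICU day T, the number of complete detailed fluid days is min(3, T - 1 - k). Days 0-2 are complete at the end of ICU day 3 + k, and day 7 at the end of ICU day 8 + k.

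| Lag k | Complete days of 0-2, transfer on ICU day 4 | Days 0-2 complete at end of ICU day | Day 7 complete at end of ICU day |
|---|---|---|---|
| 0 | 3 | 3 | 8 |
| 1 | 2 | 4 | 9 |
| 2 | 1 | 5 | 10 |
| 3 | 0 | 6 | 11 |

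The filter matches the window only when k = 0. The k = 2 row is feasible under the requirement of more than 24 hours of ventilation: start early on ICU day 3, transfer late on ICU day 4. The k = 3 row arises only if ventilation in the receiving ICU counts towards the 24 hours. The same patient transferred on ICU day 5 has 5 - 1 - 3 = 1 complete day.

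**2. Seven-day volume.** Assume constant daily volume. With d of 7 days observed, the share captured is d/7: 3/7 = 43%, 4/7 = 57%, 5/7 = 71%, 6/7 = 86%. If fluid is given mainly in the early days, the share is higher. If ventilation started late, fewer days are observed and the share is lower.

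**3. Secondary endpoints.** Setting Section 6.1.2 beside Section 6.2.3 gives two groups.
- Recorded up to ICU discharge, so available for a transferred patient: vasopressor start, route and type, and daily diuretic use.
- Cut short or possibly lost: seven-day fluid balance, later urine output, ventilation duration, ventilator-free days, lengths of stay, and deaths after a move to another hospital.

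Section 8.2 treats both groups alike.

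**4. Mortality.** The protocol gives neither the share f transferred nor their mortality m, so both are assumed: f = 2%, 5%, 10% and m = 15%, 30%, 45%. True mortality is set at 30%, the figure that Section 5.5 uses for ARDS. Apparent mortality after exclusion is (0.30 - f × m)/(1 - f).

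| f | m = 15% | m = 30% | m = 45% |
|---|---|---|---|
| 2% | 30.3% | 30.0% | 29.7% |
| 5% | 30.8% | 30.0% | 29.2% |
| 10% | 31.7% | 30.0% | 28.3% |

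For example, (0.30 - 0.10 × 0.15)/0.90 = 0.285/0.90 = 31.7%. The shift is under 2 points throughout, and its sign depends on m.

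**5. Sample size.** The figures in Section 5.5 reproduce: 150/(0.20 × 0.30) = 2500 patients and 2500/(50 × 0.25) = 200 ICUs. They make no allowance for excluded transfers. If 2%, 5% or 10% are dropped at equal mortality, expected ARDS deaths are 150 × (1 - f) = 147, 142.5 or 135.

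**The case against.** **The rule is partly sensible.** Transfer does cut short fluid balance, urine output, ventilation duration and lengths of stay, and excluding incomplete records from those can be defended. The three-day cut-off plainly aims at the detailed fluid window, and keeping later transfers is right for that component when days 0-2 are complete. This stands. A reader might infer that the rule is simply the wrong way round; the protocol does not support that. The fault is one rule for unlike endpoints.

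**Mortality is not singled out.** It goes with every other secondary endpoint. A reader might also infer that mortality is biased upward because those removed were alive at transfer. That needs transferred patients to have lower mortality than the rest, and the protocol does not say so.

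**No LMIC/HIC mortality contrast is announced.** A reader might infer that unequal transfer rates would create a spurious mortality gap in the main comparison. Section 3.1 makes description of practice the primary aim, the LMIC/HIC comparison there concerns fluid and vasopressor therapy, and no transfer rates are given by region.

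**The seven-day total is stated as primary only in the Summary.** Section 6.1.1 gives "Quantity, timing and type of intravenous fluids administered" without a window. That is so, but nothing in Section 6.1.1 withdraws the Summary's definition, and Section 6.2.3 collects the volumes for it.

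**Truncation is not peculiar to transfers.** Deaths and ICU discharges before day 7 are cut short too. This stands and shapes the fix.

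**The frequency of late ventilation followed by early transfer is unknown.** It may be small. That limits the size of the clock problem, not its existence.

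**Details belong in later analysis plans.** Section 8.2 promises one for each analysis, and missing-data handling can wait for it. The exclusion rule, however, is already fixed here, and an analysis plan that follows it inherits the mismatch.

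**Conclusion.** The point holds as an analysis rule that should be changed. Three parts rest on the protocol's text and day counting alone: the transfer cut-off and the endpoints use different origins, so the filter does not secure study days 0-2; later transfers remain in the primary analysis with an incomplete seven-day volume; and secondary data recorded before transfer are discarded.

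The mortality part is weaker. Exclusion selects on an event after enrolment that requires survival to that point, so bias is possible, but its size and direction cannot be derived from the protocol. The range of 28.3% to 31.7% around a true 30% rests entirely on assumed transfer shares and assumed mortality. The 43% to 86% for the seven-day volume rests on assumed constant daily volume.

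**What to change.** Replace the two transfer sentences in Section 8.2 with a rule set by endpoint:

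- (a) Time transfer from study day 0, the day ventilation starts.
- (b) For the three-day total, exclude only patients transferred before the end of day 2.
- (c) For the seven-day total, treat days after transfer as missing or analyse volume per observed ICU day, handled consistently with early deaths and ICU discharges. Do not restrict to patients with seven complete days: that would drop everyone who died or left the ICU early, which is again selection on prognosis.
- (d) Keep transferred patients in secondary endpoints recorded before transfer, notably vasopressor start, type and route.
- (e) For mortality, keep patients whose in-hospital vital status remains observable, such as same-hospital transfers. For the rest, run sensitivity analyses counting them all as alive and all as dead, instead of excluding them.

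The two extremes in (e) differ by exactly the unresolved share of the analysed cohort: 2 points if 2% are unresolved, 10 points if 10% are. Knowing the destination keeps that interval narrow.

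The cost is a rewritten paragraph and slightly more analysis work. The item list in Section 6.2.3 has ICU and hospital discharge dates but no transfer destination, so the sponsor must confirm that the CRF captures transfer date and destination. If vital status is known and these patients stay in the mortality analysis, the planned 2500 need not change on this account.

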5.5. Sample size calculation

No formal sample size calculation is necessary for the primary endpoint. However, for investigating associations of aspects of fluid and vasopressor therapy with mortality using logistic regression and adjusting for a limited set of pre-specified confounders, we estimate to need 150 ‘events’ using the 10 event per variable rule of thumb. As fluid and vasopressor management is particularly important in patients with acute respiratory distress (ARDS), we will need at least 150 events in this subgroup. With an incidence of ARDS of approximately 20% and a mortality rate of 30%, we estimate to need 2500 patients to have 150 events in patients with ARDS (37). Assuming that a participating ICU has 50 unique admissions in 4 weeks on average, of which 25% is invasively ventilated for > 24 hours, we expect to need a minimum of 200 participating ICUs (38-40).

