- Heart rate, beats/min, at a convenient fixed time point;
- Atrial fibrillation or flutter during the last day, yes/no;
- Arterial or venous lactate, if measured, mmol/L , highest and lowest value;
- (Central) venous oxygen saturation ($S(c)VO_2$), mmol/L , if measured, highest and lowest value;
- Arterial partial pressure of oxygen (PaO_2), kPa or mmHg , at a convenient fixed time point;
 - (if no PaO_2 is known) Peripheral arterial oxygen saturation (SpO_2), percentage, at a convenient fixed time point;
- Inspired oxygen fraction, %, at time of PaO_2 or (if no PaO_2 is known) SpO_2 ;
- Suspected or confirmed infection that causes organ dysfunction (sepsis) yes/no;
- Was there new-onset (<7 days) respiratory symptoms, or acute worsening of respiratory symptoms?, yes/no, if yes;
- Are there bilateral opacities on chest imaging (including lung ultrasound), yes/no;
- If there was hypoxemia, was the hypoxemia explained by cardiac failure, yes/no?

- Richmond Agitation Sedation Scale (RASS), highest value of this day after intubation; and
- Sequential Organ Failure Assessment (SOFA) score.

C. Daily on day 1 and day 2;

- Type, volume, ml, and rate, ml/min, of each separate fluid infusion (including medication and parenteral nutrition);
- Type and volume of oral fluids;
- Anuria \geq 12 hours?, yes/no;
- Urine output, ml, over 24 hours;
- Extracorporeal life support, venoarterial/venovenous/no;
- Renal replacement therapy, yes/no, if yes;
 - Volume extracted by ultrafiltration, ml, over 24 hours;
- Cumulative fluid balance, ml;
- Loop diuretics given, yes/no, if yes;
 - Furosemide, yes/no, if no;
 - (if no furosemide used) Bumetanide, yes/no, if no;
 - (if no bumetanide or furosemide used) Torasemide, yes/no;
 - (if no Torasemide, bumetanide, furosemide used) Edecrin, yes/no;
 - Additional diuretic given (thiazide, carbonic anhydrase inhibitor or mineralocorticoid antagonist), yes/no;
- Serum creatinine, $\mu\text{mol/L}$ or mg/dL , at a convenient fixed time point;
- Serum hemoglobin, $\mu\text{mol/L}$ or mg/dL , at a convenient fixed time point;
- Serum albumin, at a convenient fixed time point;
- Vasopressors given, yes/no, if yes;
 - Time between ICU admission and initiation of vasopressors, only if not initiated on day 0, hours;
 - Drug(s) used as vasopressor;
- MAP, mmHg, at a convenient fixed time point;
- Heart rate, beats/min, at a convenient fixed time point;
- Atrial fibrillation or flutter during the last day, yes/no;

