- Arterial or venous lactate, mmol/L , at a convenient fixed time point;
- Serum sodium, mmol/l , at a convenient fixed time point;

- Serum chloride, mmol/l, at a convenient fixed time point;
-
- S(c)VO₂, mmol/L, highest and lowest value;
- PaO₂, kPa or mmHg, at a convenient fixed time point;
- (if no PaO₂ is known) Peripheral arterial oxygen saturation (SpO₂), percentage, at a convenient fixed time point;
- Inspired oxygen fraction, %, at time of PaO₂ or (if no PaO₂ is known) SpO₂;
- Was there new-onset (<7 days) respiratory symptoms, or acute worsening of respiratory symptoms?, yes/no, if yes;
- Are there bilateral opacities on chest imaging (including lung ultrasound), yes/no;
- If there was hypoxemia, was the hypoxemia explained by cardiac failure, yes/no?
- Richmond Agitation Sedation Scale (RASS), highest value of the day; and
- SOFA score.

D. Daily on day 3 to 7 or ICU discharge; and on day -1, day -2 and day -3;

- Total volume of infused fluid, ml, over 24 hours
- Cumulative fluid balance, ml, over 24 hours;
- Urine output, ml, over 24 hours;
- Extracorporeal life support, venoarterial/venovenous/no;
- Renal replacement therapy, yes/no, if yes;
 - Volume extracted by ultrafiltration, ml, over 24 hours;
- Loop diuretics given, yes/no, if yes;
 - Furosemide, yes/no, if no;
 - (if no furosemide used) Bumetanide, yes/no, if no;
 - (if no bumetanide or furosemide used) Torasemide, yes/no;
 - (if no Torasemide, bumetanide, furosemide used) Edecrin, yes/no;
 - Additional diuretic given (thiazide, carbonic anhydrase inhibitor or mineralocorticoid antagonist), yes/no;
- Serum creatinine, µmol/L or mg/dL, at a convenient fixed time point;
- Serum hemoglobin, µmol/L or mg/dL, at a convenient fixed time point;
- Serum albumin, at a convenient fixed time point;
- Vasopressors used, yes/no, if yes;
 - Drug(s) used as vasopressor;

- MAP, mmHg, at a convenient fixed time point;
- Heart rate, beats/min, at a convenient fixed time point
- Atrial fibrillation or flutter during the last day, yes/no;
- Arterial or venous lactate, mmol/L, at a convenient fixed time point;
- Serum sodium, mmol/l, at a convenient fixed time point;
- Serum chloride, mmol/l, at a convenient fixed time point;
- PaO₂, kPa or mmHg, at a convenient fixed time point;
- (if no PaO₂ is known)) Peripheral arterial oxygen saturation (SpO₂), percentage, at a convenient fixed time point;
- Inspired oxygen fraction, %, at time of PaO₂ or (if no PaO₂ is known) SpO₂; and
- SOFA score.

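### The sepsis and ARDS subgroups are set on ICU-admission days but classified from items collected on ventilation days, and sepsis first arising on study day 1 or 2 has no field

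*Protocol*

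**What the plan says.** Section 8.2 sets the subgroup rule: "Subjects diagnosed with sepsis or ARDS during the first three calendar days of ICU admission will be part of a subgroup analysis".

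Section 6.2.3 counts study days from ventilation: "Day 0 is defined as the day of initiation of invasive ventilation". It also provides for patients who are intubated later in their stay: "In patients that are not invasively ventilated at ICU admission day -3 to -1 are defined as the days before intubation but after ICU admission". This matches section 5.2, which requires "receiving invasive ventilation within 3 days of ICU admission; and" more than 24 hours of ventilation. The protocol therefore expects ICU admission and day 0 to lie up to three days apart.

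The items that identify the two conditions are spread over section 6.2.3 as follows.

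- **ARDS.** The questions on new or worsening respiratory symptoms, bilateral opacities and a cardiac explanation are in part B (day 0) and part C (days 1 and 2). Part D, headed "D. Daily on day 3 to 7 or ICU discharge; and on day -1, day -2 and day -3", has none of the three. It does have PaO2 or SpO2, inspired oxygen fraction and SOFA.
- **Sepsis.** The item "Suspected or confirmed infection that causes organ dysfunction (sepsis) yes/no" is in part B only. Part A records the reason for ICU admission, with a follow-up question for sepsis: "If the reason for ICU admission was sepsis, what was the focus of the sepsis (e.g. respiratory, abdominal". Part E asks for the pathogen, again only in patients admitted for sepsis.

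Section 5.5 sizes the study on ARDS: "we will need at least 150 events in this subgroup".

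**The concern.** A subgroup rule can be applied only if the data needed to apply it are collected over the period it names. Here the rule names one period and the case report form covers another. The two agree for ARDS only when ventilation starts on the first ICU calendar day.

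For patients intubated later, part of the window has no imaging, onset or cardiac-origin entry, while some or all of the recorded ARDS days lie after the window has closed. Read literally, section 8.2 would leave out a patient who plainly meets the criteria on a recorded day, merely because that day is ICU day 4 or later.

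The sepsis problem is of a different kind. For sepsis that begins after admission there is a single day of observation. A patient who becomes septic the day after intubation, well inside the stated window, would be analysed as non-septic.

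At stake are the composition of both subgroups and how well the sepsis and non-sepsis groups are separated.

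**Working it through.** **Inputs.** Subgroup window: ICU calendar days 1 to 3 (section 8.2), taking the admission date as ICU day 1. ARDS items: study days 0, 1 and 2; sepsis item: study day 0 (section 6.2.3). Latest intubation: three days after admission, that is ICU day 4 (section 5.2 and the definition of days -3 to -1).

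**Mapping the clocks.** Let k be the ICU day on which ventilation starts. Study day d falls on ICU day k + d. The ARDS items are therefore recorded on ICU days k, k + 1 and k + 2, and the sepsis item on ICU day k. For k = 1 to 4, the number of window days with ARDS items is 4 - k.

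| Intubated on ICU day k | ICU days with ARDS items | Window days covered, ARDS items | Recorded ARDS days outside window | Window days covered, sepsis item |
|---|---|---|---|---|
| 1 | 1, 2, 3 | 3 of 3 | 0 | 1 of 3 |
| 2 | 2, 3, 4 | 2 of 3 | 1 | 1 of 3 |
| 3 | 3, 4, 5 | 1 of 3 | 2 | 1 of 3 |
| 4 | 4, 5, 6 | 0 of 3 | 3 | 0 of 3 |

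A smaller mismatch arises if ventilation starts on the date before ICU admission. Section 5.3 bars this only for patients transferred from another ICU. ICU day 3 is then study day 3, which belongs to part D, and ARDS coverage is 2 of 3.

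**Who is left out for ARDS under the literal rule.** With k = 2, a patient whose criteria are first met on study day 2. With k = 3, one whose criteria are first met on study day 1 or 2. With k = 4, everyone, because all recorded ARDS days are ICU days 4 to 6. With k = 1, nobody.

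**Sepsis when the clocks agree.** With k = 1, ICU days 2 and 3 are study days 1 and 2. Part C has no sepsis item. The daily SOFA score shows organ dysfunction but not infection, so sepsis cannot be rebuilt from it.

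**The plan's own figure.** 150 / (0.20 × 0.30) = 2500 patients. Each ICU yields 50 × 0.25 = 12.5 patients, and 2500 / 12.5 = 200 ICUs. Both figures reproduce exactly, with no reserve. All 150 events are ARDS events, so sepsis does not enter the calculation.

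**The case against.** The strongest reply is that little information is really lost, and several stronger readings do fail.

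- **A reader might infer that sepsis is known only from day 0.** It is not. Sepsis as the reason for admission is recorded in part A, and that falls inside the ICU-day window whatever the day of intubation.
- **A reader might infer that nothing relevant is recorded before intubation.** Oxygenation and SOFA are recorded on days -3 to -1. What is absent on those days is imaging, symptom onset, cardiac origin and infection.
- **The day-0 items look back.** The respiratory question covers onset in the preceding week (under 7 days), which spans the pre-intubation ICU stay. The sepsis question asks whether sepsis is present, not whether it is new. Disease that began earlier and persists can be picked up on day 0. What is then missing is mainly its date, so the table's day counts are not a measure of patients lost.
- **A reader might infer that late-intubated ARDS patients all drop out.** Only those intubated on ICU day 4 have every recorded ARDS day outside the window.
- **A reader might infer that the study falls short of its 150 events.** The protocol gives no distribution of intubation day or ARDS onset. If one assumes that 5% to 30% of ARDS patients cannot be placed in the window, with the same mortality as the rest, events become 150 × 0.95 = 142.5 down to 150 × 0.70 = 105. No value in that range has support in the protocol, and the true share may be close to zero.

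All of these points stand. It can also be said that a later analysis plan could move the window. For ARDS that is correct, since days 0 to 2 are fully recorded. For sepsis it is not: an analysis plan cannot recover a status on days 1 and 2 that was never collected.

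**Conclusion.** The point holds in a limited form. For ARDS it is an inconsistency between the subgroup rule and the collection schedule. It affects patients not intubated on ICU day 1, and rewording settles it without new data. For sepsis it is a gap in data collection: in patients not admitted for sepsis, onset on study day 1 or 2 has no field, whatever the day of intubation.

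The size can be stated only as window coverage, not as a number of patients or events. The 2500 patients and 200 ICUs are correctly calculated, and nothing here shows that they are too few.

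The coverage counts assume that the admission date is ICU day 1. If the window were counted from the day after admission, intubation 0, 1, 2 or 3 days after admission would give ARDS coverage of 2, 3, 2 or 1 of 3 days. The mismatch moves but does not disappear.

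That section 8.2 is the passage to change, rather than section 6.2.3, is supported by the protocol's summary, which counts the first three days of the primary fluid outcome from the start of ventilation.

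**What to change.** In section 8.2, replace the single rule with two definitions on the ventilation clock:

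- **ARDS subgroup:** criteria met on study day 0, 1 or 2, with day 0 the day of intubation.
- **Sepsis subgroup:** sepsis as the reason for ICU admission, or the sepsis item positive on study day 0, 1 or 2.

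In section 6.2.3, add the existing yes/no sepsis item to part C (days 1 and 2). The admission-reason arm must stay in the sepsis definition; without it, a patient admitted for sepsis whose item is negative from day 0 onwards would be lost.

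The cost is a rewritten sentence and one extra yes/no field on two days. The meaning shifts slightly: for a patient intubated on ICU day 4, the window becomes ICU days 4 to 6, and the report should say so. The label of the secondary parameter on ARDS incidence need not change, although stating that its imaging and onset items cover days 0 to 2 would help readers.

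If the field can no longer be added, the sepsis subgroup should be described as sepsis at admission or on day 0.
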